8.2.4.2. Change in Height SDS

The summary statistics of measured values of height SDS at each age will be calculated for the efficacy analysis set and eligible criteria set. The evaluation points are according to [Appendix A1.1](#) Definition of timing for visit 1. The change in height SDS will be plotted with a solid line for individual male and female patients separately, with age on the horizontal axis and height SDS on the vertical axis. The start of treatment will be indicated as ▲, pubescence as ●, and reaching adult height (near final height) as ▼. They will be plotted with a dotted line after the completion/discontinuation of treatment.

The same calculation will be performed to prepare plots in the same manner for the set of patients who reached adult height (near final height) and set of patients not reached.

The summary statistics of measured values of height SDS at each evaluation point and change from the start of Genotropin will be calculated for a set of patients who reached adult height (near final height). The 95% confidence interval of the mean of the change will be calculated. The evaluation points are according to [Appendix A1.2](#) Definition of timing for visit 2. The change in height SDS will be plotted with a solid line for individual male and female patients separately, with evaluation points on the horizontal axis and height SDS on the vertical axis. The start of treatment will be indicated as ▲, pubescence as ●, and reaching adult height (near final height) as ▼. They will be plotted with a dotted line after the completion/discontinuation of treatment.

The summary statistics of measured values of height SDS at each evaluation point and changes from the start of Genotropin will be calculated in the efficacy analysis set and eligible criteria set. The 95% confidence interval of the mean of the change will be calculated. The evaluation points are according to [Appendix A1.3](#) Definition of timing for visit 3. The change in height SDS will be plotted with a solid line for individual male and female patients separately, with evaluation points on the horizontal axis and height SDS on the vertical axis. The start of treatment will be indicated as ▲, pubescence as ●, and reaching adult height (near final height) as ▼. They will be plotted with a dotted line after the completion/discontinuation of treatment.

The same calculation will be performed to prepare plots in the same manner for the set of patients not reached adult height (near final height).

Additionally, a plot will be prepared with the change in the dose per week/kg after the start of Genotropin on the horizontal axis and change in height SDS after the start of Genotropin on the vertical axis. The evaluation points of the change are according to [Appendix A1.3](#) Definition of timing for visit 3. Furthermore, a plot will be prepared with the change in the dose per week/kg from the previous year on the horizontal axis and the change in height SDS from the previous year on the vertical axis.

8.2.4.3. Change in Height Velocity

The summary statistics of measured values of height velocity at each evaluation point and change from the start of Genotropin will be calculated for the efficacy analysis set and eligible criteria set. Further, the 95% confidence interval of the mean of the change will be calculated. The evaluation points are according to [Appendix A1.3](#) Definition of timing for visit 3. The change in height velocity will be plotted with a solid line for individual male and female patients separately, with evaluation points on the horizontal axis and height velocity on the vertical axis. The start of treatment will be indicated as ▲, pubescence as ●, and reaching adult height (near final height) as ▼. They will be plotted with a dotted line after the completion/discontinuation of treatment.

The same calculation will be performed to prepare plots in the same manner for the set of patients not reached adult height (near final height).

8.2.4.4. Change in Height Velocity SDS

The summary statistics of measured values of height velocity at each evaluation point and changes from the start of Genotropin will be calculated in the efficacy analysis set and eligible criteria set. Further, the 95% confidence interval of the mean of the change will be calculated. The evaluation points are according to [Appendix A1.3](#) Definition of timing for visit 3. The change in height velocity SDS will be plotted with a solid line for individual male and female patients separately, with evaluation points on the horizontal axis and height velocity SDS on the vertical axis. The start of treatment will be indicated as ▲, pubescence as ●, and reaching adult height (near final height) as ▼. They will be plotted with a dotted line after the completion/discontinuation of treatment.

The same calculation will be performed to prepare plots in the same manner for the set of patients not reached adult height (near final height).

8.2.4.5. Change in Body Weight SDS

The summary statistics of measured values of body weight SDS at each age will be calculated for the efficacy analysis set and eligible criteria set. The evaluation points are according to [Appendix A1.1](#) Definition of timing for visit 1.

The same calculation will be performed for the set of patients who reached adult height (near final height) and set of patients not reached.

The summary statistics of measured values of body weight SDS at each evaluation point and change from the start of Genotropin will be calculated for a set of patients who reached adult height (near final height) in the eligible criteria set. Further, the 95% confidence interval of the mean of the change will be calculated. The evaluation points are according to [Appendix A1.2](#) Definition of timing for visit 2.

The summary statistics of measured values of body weight SDS at each evaluation point and changes from the start of Genotropin will be calculated in the eligible criteria set. Further, the 95% confidence interval of the mean of the change will be calculated. The evaluation points are according to [Appendix A1.3](#) Definition of timing for visit 3.

The same calculation will be performed for the set of patients not reached adult height (near final height) in the eligible criteria set.

8.2.4.6. Change in BMI SDS

The summary statistics of measured values of BMI SDS at each age will be calculated in the efficacy analysis set and eligible criteria set. The evaluation points are according to [Appendix A1.1](#) Definition of timing for visit 1.

The same calculation will be performed for the set of patients who reached adult height (near final height) and set of patients not reached.

The summary statistics of measured values of BMI SDS at each evaluation point and change from the start of Genotropin will be calculated for a set of patients who reached adult height (near final height) in the eligible criteria set. Further, the 95% confidence interval of the mean of the change will be calculated. The evaluation points are according to [Appendix A1.2](#) Definition of timing for visit 2.

The summary statistics of measured values of BMI SDS at each evaluation point and change from the start of Genotropin will be calculated in the eligible criteria set. Further, the 95% confidence interval of the mean of the change will be calculated. The evaluation points are according to [Appendix A1.3](#) Definition of timing for visit 3.

The same calculation will be performed for the set of patients not reached adult height (near final height) in the eligible criteria set.

8.2.4.7. Change in IGF-I SDS

The summary statistics of measured values of IGF-I SDS at each age will be calculated in the efficacy analysis set and eligible criteria set. The evaluation points are according to [Appendix A1.1](#) Definition of timing for visit 1.

The same calculation will be performed for the set of patients who reached adult height (near final height) and set of patients not reached.

The summary statistics of measured values of IGF-I SDS at each evaluation point and change from the start of Genotropin will be calculated for a set of patients who reached adult height (near final height) in the eligible criteria set. Further, the 95% confidence interval of the mean of the change will be calculated. The evaluation points are according to [Appendix A1.2](#) Definition of timing for visit 2.

The summary statistics of measured values of IGF-I SDS at each evaluation point and change from the start of Genotropin will be calculated in the eligible criteria set. Further, the 95% confidence interval of the mean of the change will be calculated. The evaluation points are according to [Appendix A1.3](#) Definition of timing for visit 3.

The same calculation will be performed for the set of patients not reached adult height (near final height) in the eligible criteria set.

8.2.4.8. Subset Analysis

A subset analysis of the change in height SDS will be performed by the factors specified in 5.4.

8.2.4.9. CCI

[REDACTED]

[REDACTED]

[REDACTED]

[REDACTED]

[REDACTED]

9. LISTS

The following lists will be prepared.

- Patient list.
- List of patients with adverse events.
- List of patients with adverse drug reactions.
- List of patients with adverse drug reactions excluded from safety analysis set.
- List of patients with serious adverse drug reactions.
- List of patients with serious adverse events.
- List of laboratory test parameters.

11. APPENDIXES

11.1. Appendix 1: Details of Data Extraction

A1.1 DEFINITION OF TIMING FOR VISIT 1

Timing for visit	Endpoint	Definition [allowable range]
3 years	Height Height SDS Body weight SDS BMI SDS IGF-I SDS	3 years and 0 month to 3 years and 11 months
4 years	Height Height SDS Body weight SDS BMI SDS IGF-I SDS	4 years and 0 month to 4 years and 11 months
N years	Height Height SDS Body weight SDS BMI SDS IGF-I SDS	N years and 0 month to N years and 11 months

The measured value on the latest date will be used when the same patient receives more than one measurement during the same visit.

A1.2 DEFINITION OF TIMING FOR VISIT 2

Timing for visit	Endpoint	Definition [allowable range]
Start of Genotropin therapy	Height SDS Body weight SDS BMI SDS IGF-I SDS	90 days before the first date of treatment (the start date of treatment) to the start date of treatment for this investigation
Pubescence	Height SDS Body weight SDS BMI SDS IGF-I SDS	The date evaluated as the pubescence +90 days
At reaching adult height (near final height)	Height SDS Body weight SDS BMI SDS IGF-I SDS	The date evaluated to reach adult height (near final height) +90 days

The measured value on the earliest date will be used when the same patient receives more than one measurement during the same visit.

In this regard, all the data measured after reaching adult height (near final height) will be used if plots are prepared.

A1.3 DEFINITION OF TIMING FOR VISIT 3

Timing for visit	Endpoint	Definition [allowable range]
Start of Genotropin therapy	Laboratory test parameters Height SDS Height velocity Height velocity SDS Body weight SDS BMI SDS IGF-I SDS	90 days before the first date of treatment (the start date of treatment) to the start date of treatment for this investigation
1 year later	Laboratory test parameters Height SDS Height velocity Height velocity SDS Body weight SDS BMI SDS IGF-I SDS	365 ±90 days after the start of treatment
2 years later	Laboratory test parameters Height SDS Height velocity Height velocity SDS Body weight SDS BMI SDS IGF-I SDS	730 ±90 days after the start of treatment
N years later	Laboratory test parameters Height SDS Height velocity Height velocity SDS Body weight SDS BMI SDS IGF-I SDS	365 × N ±90 days after the start of treatment
Completion of Genotropin therapy	Laboratory test parameters Height SDS Height velocity Height velocity SDS Body weight SDS BMI SDS IGF-I SDS	Final date of treatment for this investigation (completion date of treatment) ±90 days

Timing for visit	Endpoint	Definition [allowable range]
Completion of height follow-up	Height SDS Height velocity Height velocity SDS Body weight SDS BMI SDS	Completion date of height follow-up ± 90 days

The measured value on the earliest date will be used when the same patient receives more than one measurement during the same visit.

In this regard, all the data measured after the completion of height follow-up will be used if plots are prepared.

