6.5. Examinations/tests (clinical laboratory/clinical course)

Results of the following parameters tested will be recorded until the completion of assessment period for each booklet; provided that Booklet 01 should include the results prior to the commencement of Genotropin therapy. Of the results of examinations and tests performed prior to the commencement of Genotropin therapy, those within 1 month prior to the commencement of Genotropin therapy should be recorded (including the date the Genotropin therapy is commenced).

- [1] Carbohydrate metabolism related tests (fasting or continuous glucose, HbA1c), serum lipid concentration (total cholesterol, triglyceride), thyroid function related tests (TSH, free T4), and IGF-I
- [2] Height (to the first decimal place), weight (to the first decimal place), and head circumference (to the first decimal place)
- [3] Pubescence
- [4] Bone age
- [5] Body composition

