6.2. Efficacy Endpoints

- Height.
- Height SDS: $(\text{height} - \text{standard height for chronological age/gender}^2) / \text{standard deviation}$.
- Height velocity: $365.25 \times (\text{height} - \text{height of 1 year before}) / (\text{date of height measurement} - \text{date of height measurement of 1 year before})$ (height of 1 year before: Height of the previous year as used according to “[Appendix A1.3](#) Definition of timing for visit 3”).
- Height velocity SDS: $(\text{height velocity} - \text{mean height velocity for chronological age/gender}^3) / \text{standard deviation}$.

CCI

- [REDACTED]
- [REDACTED]
- [REDACTED]

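### The SAP takes the earliest, not the last, pre-treatment value in a 90-day window as baseline; where a child has several, year-1 height velocity is diluted

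*SAP*

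**What the plan says.** Appendix A1.2 (start, pubescence, adult height) and A1.3 (start, yearly visits, completion) define the start-of-treatment window in the same words: "90 days before the first date of treatment (the start date of treatment) to the start date of treatment for this investigation". Below each table stands the same rule for repeat values: "The measured value on the earliest date will be used when the same patient receives more than one measurement during the same visit". Neither table exempts its start row. A1.1, which groups values by age and has no start row, uses the opposite rule: "The measured value on the latest date will be used when the same patient receives more than one measurement during the same visit".

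SAP 6.2 defines height velocity as the height difference over the actual number of days, scaled to 365.25 days. The earlier height is described as "Height of the previous year as used according to" A1.3. For the year-1 visit, set at "365 ±90 days after the start of treatment", that earlier height is the start-row value.

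Protocol 6.5 has a narrower recording rule. Of the results obtained before treatment, "those within 1 month prior to the commencement of Genotropin therapy should be recorded", with the start date itself included.

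**The concern.** A baseline should describe the child as close as possible to first exposure. When there are two values in the window, say on day -28 and day 0, the SAP keeps day -28 and discards the start-day value. It gives no reason. Protocol 6.5 allows both a work-up value and a start-day value to be recorded, so the situation can arise.

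Year-1 height velocity is then an average over time before and after the first Genotropin dose. If growth speeds up on treatment, that average understates the year-1 velocity. The SAP reports change from start in height velocity (8.2.4.3) and plans the velocity SDS in the same way (8.2.4.4), with 95% confidence intervals for the mean change. The changes from start in height, body weight, BMI and IGF-I SDS and in HbA1c also begin from an older value than necessary.

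**Working it through.** The documents give no figure for this effect and no growth velocities, so there is nothing to reproduce. The check applies the SAP 6.2 formula directly.

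**Inputs from the documents**
- Start window: day -90 to day 0 (A1.2, A1.3).
- Year-1 window: 365 - 90 = day 275 to 365 + 90 = day 455 (A1.3).
- Recording limit for new children: one month before start (Protocol 6.5), taken here as 30 days.

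**Assumptions**
- Velocity is v0 cm/year before and v1 cm/year after the first dose, each constant, with v1 - v0 between 1 and 5 cm/year.
- The discarded later value was on day 0, so the alternative baseline gives exactly v1.

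**Formula.** With the baseline d days before the first dose and the year-1 height on day T:
- year-1 velocity = (d × v0 + T × v1) / (d + T)
- pre-Genotropin share of the interval = d / (d + T)
- understatement = d / (d + T) × (v1 - v0)

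| d (days) | T (day) | Share | Loss if v1 - v0 = 1 | = 3 | = 5 (cm/year) |
|---|---|---|---|---|---|
| 30 | 275 | 9.8% | 0.10 | 0.30 | 0.49 |
| 30 | 365 | 7.6% | 0.08 | 0.23 | 0.38 |
| 30 | 455 | 6.2% | 0.06 | 0.19 | 0.31 |
| 90 | 275 | 24.7% | 0.25 | 0.74 | 1.23 |
| 90 | 365 | 19.8% | 0.20 | 0.59 | 0.99 |
| 90 | 455 | 16.5% | 0.17 | 0.50 | 0.83 |

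Example with v0 = 5, v1 = 8 and T = 365: at 30 days (150 + 2920) / 395 = 7.77, and at 90 days (450 + 2920) / 455 = 7.41, against 8.00 from a day-0 baseline.

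**Cohort mean.** If a fraction f of children have repeat values, the mean loss is f times the figure in the table. With f = 25%, v1 - v0 = 3 and T = 365, it is 0.06 cm/year at 30 days and 0.15 at 90 days. The documents do not give f.

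**Other outputs**
- Height SDS: the shift in the change from start is (v0 - velocity that holds SDS constant) × d / 365.25 / SD. Assuming that velocity difference lies between -2 and +0.5 cm/year and the SD is 4 to 5 cm, the shift is -0.04 to +0.01 SDS at 30 days and -0.12 to +0.03 at 90 days. It is small and its sign is uncertain.
- Height in cm: the gain from start rises by v0 × d / 365.25. For v0 of 4 to 6 cm/year that is 0.33 to 0.49 cm at 30 days and 0.99 to 1.48 cm at 90 days. SAP 8.2.4.1 uses gain from start only in a plot against dose change; its summary statistics for height are by age under A1.1.
- Height velocity from year 2: both heights come from post-start visits, so no pre-start time enters that term. The start velocity it is compared with (8.2.2) is a pre-Genotropin velocity under either rule.

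**The case against.** Four points against the concern have force.

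- **Few children may be affected.** With one value in the window, the earliest and the last are the same. Nothing shows how many children have two, or that the later one usually falls on the start day. The tabulated losses are per affected child.
- **Ninety days is not the expected case for new children.** Protocol 6.5 asks only for the last month. A longer gap needs older values to have been recorded. That is conceivable for children transferred from the earlier investigation, whose data enter the analysis (SAP 2.1), but the recording rule there is not in the documents. The 24.7% figure also needs the year-1 visit on day 275, the edge of its window.
- **Pre-start weeks are not always untreated.** Protocol 6.2 records growth hormone used up to the day before Genotropin began. For a child who switched, those weeks are pre-Genotropin but treated, and the assumed 1 to 5 cm/year difference need not apply.
- **No decision depends on it.** SAP 4.1 treats testing as exploratory with no significance level, and 4.2 has no decision rule.

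All four stand. They limit the size of the effect, but none gives a reason to prefer the older of two available values.

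A reader might infer that untreated weeks enter every change from start. The documents do not support that: height velocity from year 2 is clear of them in its post-start term, and the by-age summaries use A1.1. Nor do they support an inference that the main height tables overstate gain in cm, since that quantity appears only in the dose-change plot.

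**Conclusion.** The concern holds in a limited form. A stated rule picks the less suitable baseline whenever a child has more than one value from day -90 to day 0. The result of any size is year-1 height velocity and its SDS. For an affected child with a later value on day 0 and the year-1 visit on day 365, velocity is understated by about 0.08 to 0.38 cm/year at a 30-day gap, the realistic case for new children, and by 0.20 to 0.99 at 90 days, which is possible only if older values were recorded. Both ranges rest on the assumed velocity difference. The velocity SDS moves the same way, but the documents give no SD from which to size it.

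Body weight, BMI and IGF-I SDS and HbA1c have an older baseline than necessary, with no size that the documents allow one to state. Severity is minor to moderate: a modest bias in descriptive means and their confidence intervals.

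**What to change.** In the start row of A1.2 and A1.3, state that the last measurement on or before the first Genotropin date is used. Limit the present earliest-date sentence to the remaining rows; whether it suits those rows is a separate question.

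Reconcile the SAP's 90-day window with the protocol's one-month recording rule: either align them, or say why 90 days is kept, for instance for transferred children's data. Shortening the window has a price, because SAP 7 treats values outside the acceptable range as missing without imputation, so a child whose only value is older than one month would lose the baseline.

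The change of rule costs one sentence per table and a re-run of the derived baselines, with no new data. It does not help a child whose only value lies early in the window. Reporting the distribution of days from baseline height to first dose, and the number of children with repeat values, would show how much remains.

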For patients transferring from "Genotropin Special Investigation - Investigation of Genotropin long-term use in patients with SGA dwarfism without epiphyseal closure," the initial fiscal assessment period will be defined as a period starting on the day following the final assessment of data recorded in the last booklet for "Genotropin Special Investigation - Investigation of Genotropin long-term use in patients with SGA dwarfism without epiphyseal closure" and ending with the fiscal end of the applicable year. The fiscal assessment period of each subsequent year will be defined as the corresponding annual fiscal period.

For ongoing subjects, data collected during the "Genotropin Special Investigation - Investigation of Genotropin long-term use in patients with SGA dwarfism without epiphyseal closure" are included in the analysis set.

Height follow-up period

Patients completing or discontinuing Genotropin therapy will be followed up to document body heights from the completion or discontinuation of Genotropin therapy to the completion of investigation or until reaching adult height (final assessment). The follow-up period for each booklet will correspond to each fiscal year.

Target sample size

The target number of subjects from which data will be collected is approximately 400.

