8.2.3.4. CCI

8.2.4. Efficacy Analysis

8.2.4.1. Change in Height

The summary statistics of measured values of height at each age will be calculated for the efficacy analysis set and eligible criteria set. The evaluation points are according to [Appendix A1.1](#) Definition of timing for visit 1. The change in height will be plotted with a solid line for individual male and female patients separately, with age on the horizontal axis and height on the vertical axis. On the plot, the plots of the standard height and standard height ± 1 SD, ± 2 SD, -2.5 SD, and -3 SD will be superimposed using a dotted line as a reference line for male and female patients, separately. The start of treatment will be indicated as ▲, pubescence as ●, and reaching adult height (near final height) as ▼. They will be plotted with a different dotted line from that used for the reference line after the completion/discontinuation of treatment.

The same calculation will be performed to prepare plots in the same manner for the set of patients who reached adult height (near final height) and set of patients not reached.

Additionally, a plot will be prepared with the change in the dose per week/kg after the start of Genotropin on the horizontal axis and change in height after the start of Genotropin on the vertical axis. The evaluation points of the change are according to [Appendix A1.3](#) Definition of timing for visit 3. Furthermore, a plot will be prepared with the change in the dose per

week/kg from the previous year on the horizontal axis and the change in height from the previous year on the vertical axis.

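### SAP A1.3 takes the earliest value in a symmetric ±90-day yearly window, so the mean year-1 change in height SDS tends to be understated while height SDS is still rising; the size depends on visit timing that the documents do not give

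*SAP*

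**What the plan says.** SAP Appendix A1.3 defines the first yearly point as "365 ±90 days after the start of treatment" and later ones as "365 × N ±90 days after the start of treatment". Year 1 therefore runs from day 275 to day 455. For more than one value in a window the rule is: "The measured value on the earliest date will be used when the same patient receives more than one measurement during the same visit". Appendix A1.1, which groups values by age, takes the latest value instead. No reason is given for either choice, and no row takes the value nearest its target.

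SAP 8.2.4.2 uses the A1.3 points for height SDS: summary statistics of values and "changes from the start of Genotropin will be calculated in the efficacy analysis set and eligible criteria set". It adds: "The 95% confidence interval of the mean of the change will be calculated". SAP 8.2.4.1 also uses them for a plot against dose change, with "change in height after the start of Genotropin on the vertical axis".

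The documents set no visit interval. Protocol 6.5 says only: "Results of the following parameters tested will be recorded until the completion of assessment period for each booklet".

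**The concern.** In a window centred on day 365N, picking the first value is one-sided. It can move the chosen day earlier than the nearest available value, but never later, so the displacement does not average out across children. Change from start in height SDS is cumulative. A child measured on day 290 has had less treatment than one measured on day 365, yet both enter the year-1 mean. Nothing in 8.2.4.2 divides by elapsed time or reports the day used.

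The confidence interval describes spread between children and does not show a shift common to them. At stake is a published year-1 figure whose typical measurement day may be nearer month 10 than month 12.

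**Working it through.** The plan gives no figure to reproduce: no visit interval, expected gain, standard deviation (SD) or bias. From the SAP come the 365N ±90-day window, the earliest-value rule and the target of about 400 subjects. Everything else below is assumed.

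**Step 1: day selected, random phase.** If visits are s days apart (s up to 180) and fall at random relative to first dose, the first visit in the window is uniform on 275 to 275 + s. Its mean is 275 + s/2.

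**Step 2: shortfall.** Take the baseline as day 0 and let g(t) be the cumulative gain in height SDS. The cohort-average shortfall is 1 − mean g(t selected) / g(365).
- Linear gain: (90 − s/2)/365. Quarterly: (90 − 45.6)/365 = 12.2%. Monthly: (90 − 15.2)/365 = 20.5%.
- Front-loaded gain: g(t) = 1 − exp(−t/τ), with τ = 365, 180 or 120 days. Quarterly with τ = 365: mean g = 0.583 against g(365) = 0.632, a shortfall of 7.7%.

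| Visits (random phase) | Mean day | Linear | τ = 365 | τ = 180 | τ = 120 |
|---|---|---|---|---|---|
| Monthly | 290 | 20.5% | 13.3% | 7.8% | 4.4% |
| 2-monthly | 305 | 16.3% | 10.4% | 6.0% | 3.3% |
| Quarterly | 321 | 12.2% | 7.7% | 4.4% | 2.4% |
| 4-monthly | 336 | 8.0% | 5.1% | 3.0% | 1.7% |
| Half-yearly | 365 | 0.0% | 0.6% | 0.6% | 0.5% |

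Taking the nearest value instead gives a mean day of 365 and a shortfall of at most 0.2% for monthly to quarterly visits on all four curves. The half-yearly residual is the same under both rules.

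**Step 3: quarterly visits tied to first dose.** The third visit falls close to day 275, so a day or two decides whether it counts. Linear shortfall, with uniform scatter around each planned visit:

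| Spacing | No scatter | ±2 days | ±5 days | ±14 days |
|---|---|---|---|---|
| 90 days | 1.4% | 1.4% | 1.4% | 8.5% |
| 91 days | 0.3% | 0.3% | 7.5% | 10.0% |
| 91.25 days | 0.0% | 4.6% | 9.0% | 10.4% |
| 92 days | 24.4% | 18.0% | 14.0% | 11.7% |

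No single figure describes quarterly visits of this kind. The 1.4% at 90 days is not due to the rule, because day 360 is also the nearest value.

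**Step 4: later years.** With linear gain the shortfall is (90 − s/2)/(365N). Monthly to quarterly this is 10.2 to 6.1% at year 2 and 4.1 to 2.4% at year 5. Front-loaded gain fades faster: quarterly with τ = 180 gives 0.5% at year 2.

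**Step 5: against the confidence interval.** For an assumed year-1 gain of 0.4 to 0.8 SDS, the random-phase shift runs from 0.4 × 2.4% = 0.01 to 0.8 × 20.5% = 0.16 SDS. The half-width is 1.96 × SD/√n. With an assumed SD of 0.3 to 0.5 it is 0.029 to 0.049 at n = 400 and 0.059 to 0.098 at n = 100.

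**The case against.** The strongest reply is that everything driving the size is assumed. That stands. The multiple-value rule says what to do when several values occur; it does not show that they often do. If most children have one value per window, or are seen half-yearly, the rule changes almost nothing.

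Four stronger readings are tempting, and the documents do not support them.
- A reader might infer that measurement quarterly or more often by itself costs a fixed share of the year-1 gain. Step 3 shows otherwise: exact 91.25-day visits lose nothing, and neighbouring spacings differ widely. The 2 to 20% is a range of cohort averages under assumed patterns, not a bound.
- A reader might infer that the shift is several times the confidence-interval half-width. That pairs the largest assumed shift with the smallest SD and the full target. The SAP says "The target number of subjects from which data will be collected is approximately 400", which is not the number with both a start and a year-1 height; with fewer children or a larger SD, many of the shifts lie inside the half-width.
- A reader might extend the point to height velocity. SAP 6.2 annualises it by actual measurement dates, so no loss is claimed there. The change in height from start in 8.2.4.1 is only plotted, not tabulated.
- A reader might want every A1.2 and A1.3 row changed. Protocol 6.5 already asks for pre-treatment results from within 1 month before start. At completion of Genotropin therapy, a nearest-date rule could replace an on-treatment value with an off-treatment one. In the +90-day rows for pubescence and adult height, the earliest value already is the nearest.

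It is also fair that the rule is prespecified and reproducible, that individual curves are plotted and that height SDS is summarised by age as well. None of this corrects the tabulated year-1 mean. Height SDS standardises for age, not for time on treatment.

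**Conclusion.** The point holds as one of direction. With several values in a yearly window, the A1.3 rule selects at or before the value nearest day 365N. While height SDS is rising, the mean year-1 change in 8.2.4.2 is then understated on average, with no correction.

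The size is conditional. Random-phase monthly to quarterly visits give about 12 to 20% with linear gain and 2 to 13% with front-loaded gain. If height SDS has levelled off by about day 275, nothing is lost.

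SAP 4.1 and 4.2 set no significance level and no decision rule, so the consequence is a year-1 estimate that may be too small, not a wrong decision. It is worth correcting because the results are meant for publication and the remedy is cheap.

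**What to change.** In the yearly rows of A1.3, replace the earliest-value rule with the value nearest day 365N, taking the earlier one on ties. Report the actual measurement day (mean and range) at each yearly point, so that readers can see what year 1 means in these data. Leave the Start, Completion, pubescence and adult-height rows as they are.

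The cost is a sentence or two in the appendix and a small change in the selection code. It needs no new data and no change to visits or treatment. If visits prove to be half-yearly or exactly on schedule, the results will hardly move.
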